### **ECG**

Summary statistics and the frequencies of shifts in ECG status from baseline at 16 and 52 weeks will be tabulated for each treatment group.

## Pulse

Summary statistics and the frequencies of shifts from baseline to 16 and 52 weeks will be tabulated for each treatment group. In addition, statistical analyses similar to those made for blood pressure will be performed considering safety analysis set.

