### **Potential risks**

There is currently no evidence in humans supporting a causal relationship between liraglutide treatment and any of the following potential risks.

C-cell tumours induced in mice and rats following dosing of liraglutide are believed to be caused by a non-genotoxic, specific GLP-1 receptor-mediated mechanism to which mice and rats are particularly sensitive. The relevance for humans is likely to be low. No reports of MTC have been identified as having a clear causal relationship to liraglutide. Data from the intensive monitoring of calcitonin (a marker for MTC) in plasma in the liraglutide clinical development programmes do not support an effect of liraglutide effect on calcitonin levels in humans.

Subjects with obesity and subjects with overweight have an increased risk of certain types of cancer. In the weight management programme, the reporting rate of neoplasm events confirmed by external independent event adjudication was similar with liraglutide and placebo. Based on a limited number of reports in the weight management programme, a numerical imbalance was observed for events of breast neoplasms in females and colorectal adenomas in males.

In the clinical development programme, mean increase in resting pulse (by 2-3 beats per minute) as well as a decrease in systolic blood pressure has been observed. The long-term clinical effects of the increase in resting pulse have not been established. There was no indication that the effect on resting pulse was dose dependent. However, as the long-term clinical effects of the increase in resting pulse have not been established, cardiovascular disorders are an important potential risk also for liraglutide in weight management.

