**Table 5-2 Taxonomy for subjects based on of week 16 and 52 assessments being available or missing**

Assessment at week 16 and 52	On randomised treatment at week 16 and 52	Type description	Type abbreviation
Available	Yes	Available on randomised treatment: Subjects who did not discontinue randomised treatment prematurely with an assessment at week 16 and 52.	AT
	No	Available drop-outs: Subjects who discontinued randomised treatment prematurely but returned to have an assessment at week 16 and 52; also called retrieved drop-outs.	AD
Missing	Yes	Missing on randomised treatment: Subjects who did not discontinue randomised treatment prematurely without an assessment at week 16 and 52.	MT
	No	Missing drop-outs: Subjects who discontinued randomised treatment prematurely and did not return to have an assessment at week 16 and 52; also called non-retrieved drop-outs.	MD

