**Primary approach for handling missing values**

The primary approach for multiple imputations of missing values of BMI SDS at week 16 and 52 (type MT+MD [Table 5-2](#)) for both the liraglutide 3.0 mg and placebo group is by sampling all available assessments at respective landmark visits in the placebo group (type AT+AD). This approach is also known as jump to reference and makes the assumptions that subjects instantly after discontinuation lose any effect of randomised treatment beyond what can be expected from placebo treatment as adjunct to diet and exercise. The multiple imputation approach is done in four steps.

**Imputation:** Step 1: 1000 copies of the dataset will be generated.

**Analysis:** Step 2: Impute the missing value from placebo completers by fitting enriched regression model. Model will be fitted with the factors, covariates and interaction term in the same order as mentioned in [Table 5-3](#). The estimated parameters and their variances from this model were used to impute missing values at 16 weeks (or 52 weeks) for subjects in both treatment arms, based on their factor levels and the values of the covariates.

**Analysis:** Step 3: For each of the 1000 complete datasets, the change from baseline in BMI SDS at 16 weeks (or 52 weeks) will be analysed using the main ANCOVA model with factors and covariates and interaction term as mentioned in [Table 5-1](#).

**Pooling:** Step 4: Pool the 1000 estimation results into final result using Rubin's formula.

If N = 1000 copies are insufficient to obtain stable results, a higher number will be used.

The imputation model in step 2 uses placebo subjects from FAS with non-missing BMI SDS at baseline and 16 weeks (or 52 weeks). The imputation model is a linear regression of BMI SDS at 16 weeks (or 52 weeks) on the factors and covariates listed in [Table 5-3](#) (except randomised treatment arm) with interaction term included in the model. The order of the factors and covariates has been retained as mentioned in [Table 5-3](#) while fitting imputation model. The estimated posterior distribution for the parameters (regression coefficients and variances) in the imputation model is then used to impute missing 16 weeks (or 52 weeks) BMI SDS values for both randomised treatment arms.

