### **Other efficacy endpoints**

The following other efficacy variables will be evaluated:

- Body weight
- Waist circumference
- Waist to hip circumference ratio
- CV biomarker (hsCRP)
- Fasting lipids (TC, LDL-cholesterol, HDL-cholesterol, non-HDL cholesterol, VLDL cholesterol, TG and FFA)
- Systolic and diastolic blood pressure
- Quantitative glucose metabolism parameters (HbA1c, FPG, fasting insulin, C-peptide, HOMA-B and HOMA-IR)

The changes in these variables from baseline at 16 and 52 weeks will be analysed using the same type of ANCOVA with MI as used for the main analysis of the primary endpoint, but with the baseline value of the corresponding variable instead of the baseline BMI SDS as covariate. Each endpoint will be analysed separately. For hsCRP, fasting lipids, fasting insulin, C-peptide, HOMA B and HOMA IR, the response and baseline values will be log transformed prior to the analysis.

Categorical responses will be a binary outcome indicating for each subject whether the respective endpoint is achieved. Missing data will be handled by a MI method similar to the one used for the main analysis of the primary endpoint, but adapted to the logistic regression model. The treatment differences will be presented as odds ratios together with the associated 95% CIs.

For missing glycaemic category, the imputation will be done for missing FPG and HbA1c assessments using the imputation model mentioned in [Table 5-5](#).

In addition to all the supportive secondary efficacy analysis following added endpoints will be analysed similarly as per primary endpoint statistical model mentioned in protocol section 17.3.

- Change from baseline at 16 and 52 weeks:
  - BMI SDS (%)
  - BMI (%)

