16	Change from baseline in VLDL (mmol/L)	Week 16, Week 52	Continuous	J2R-MI ANCOVA (with log transformed response and baseline values)	FAS	NA
17	Change from baseline in TG (mmol/L)	Week 16, Week 52	Continuous	J2R-MI ANCOVA (with log transformed response and baseline values)	FAS	NA
18	Change from baseline in FFA (mmol/L)	Week 16, Week 52	Continuous	J2R-MI ANCOVA (with log transformed response and baseline values)	FAS	NA
19	Change from baseline in Systolic Blood Pressure (mmHg)	Week 16, Week 52	Continuous	J2R-MI ANCOVA	FAS	NA
20	Change from baseline in Diastolic Blood Pressure (mmHg)	Week 16, Week 52	Continuous	J2R-MI ANCOVA	FAS	NA
21	Change from baseline in HbA 1c (%)	Week 16, Week 52	Continuous	J2R-MI ANCOVA	FAS	NA

SI No.	Endpoints	Landmark visits	Endpoint type	Imputation approach and Statistical model	Analysis set	Sensitivity analyses
22	Change from baseline in FPG (mmol/L)	Week 16, Week 52	Continuous	J2R-MI ANCOVA	FAS	NA
23	Change from baseline in fasting insulin (pmol/L)	Week 16, Week 52	Continuous	J2R-MI ANCOVA (with log transformed response and baseline values)	FAS	NA
24	Change from baseline in C-peptide (nmol/L)	Week 16, Week 52	Continuous	J2R-MI ANCOVA (with log transformed response and baseline values)	FAS	NA
25	Change from baseline in HOMA-B	Week 16, Week 52	Continuous	J2R-MI ANCOVA (with log transformed response and baseline values)	FAS	NA
26	Change from baseline in HOMA-IR	Week 16, Week 52	Continuous	J2R-MI ANCOVA (with log transformed response and baseline values)	FAS	NA
27	Change from baseline in Pulse (beats/min)	Week 16, Week 52	Continuous	J2R-MI ANCOVA	SAS	NA
28	Relative change from baseline in Amylase	Week 16, Week 52	Continuous	MMRM (with log transformed response and baseline values)	SAS	NA
29	Relative change from baseline in Lipase	Week 16, Week 52	Continuous	MMRM (with log transformed response and baseline values)	SAS	NA

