## Laboratory parameters

Summary statistics will be tabulated for each laboratory parameter. The distributions will also be presented graphically using box plots by treatment and week.

For each laboratory parameter, the values will be compared to the relevant reference range. The results will be presented as follows:

- Shifts from baseline at 16 and 52 weeks will be tabulated. The shift tables will include the number of subjects below, within and above the reference range at each visit
- The proportion of subjects with laboratory values outside the reference range will be tabulated per visit and treatment group
- Individual values outside the reference range (abnormal values) will be listed by treatment and subject

For amylase and lipase the relative change ( $100 \times \text{value}/\text{baseline}$ ) will be analysed with an MMRM model as described under sensitivity analysis in section [5.3.3](#). The response and baseline values will be log transformed prior to the analysis. Safety analysis set will be considered. All lab parameters will be reported in standard units. However for the parameters like Total Cholesterol, LDL, HDL, Triglycerides, Total bilirubin, Creatinine, calcium, HbA1C, Fasting plasma glucose conventional units will also be provided along with standard units in the descriptive statistics output.

Box plots will be provided for lab parameters like Calcitonin, Lipase, Amylase, ALT, AST and Prolactin

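### Pulse, an expected harm of liraglutide, is modelled only with placebo-based (jump-to-reference) imputation, which pulls the estimated rise toward zero, and no sensitivity analysis is planned.

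*SAP*

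**What the plan says.** The SAP's Pulse paragraph (section 5.4.1.3) plans summary statistics and shift tables, and adds that "statistical analyses similar to those made for blood pressure will be performed considering safety analysis set". Blood pressure is one of the variables in SAP 5.4.1.1 whose changes "will be analysed using the same type of ANCOVA with MI as used for the main analysis of the primary endpoint". Table 5-5, row 27, "Change from baseline in Pulse (beats/min"), confirms this: J2R-MI ANCOVA, weeks 16 and 52, safety analysis set, sensitivity analyses not applicable.

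SAP 5.3.2.2 describes the imputation. Filling in missing values "for both the liraglutide 3.0 mg and placebo group is by sampling all available assessments at respective landmark visits in the placebo group". The stated assumption is that "subjects instantly after discontinuation lose any effect of randomised treatment beyond what can be expected from placebo treatment". The rule covers two types from Table 5-2: drop-outs without a landmark value (MD) and type MT, "Subjects who did not discontinue randomised treatment prematurely without an assessment at week 16 and 52". Protocol 17.3 justifies the approach as conservative for estimating the treatment effect. Neither document gives a separate rationale for a safety variable.

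Protocol 18.1, under Potential risks, reports a "mean increase in resting pulse (by 2-3 beats per minute") in the development programme and for that reason treats cardiovascular disorders as an important potential risk. For amylase and lipase, the other safety variables modelled in Table 5-5, the relative change "will be analysed with an MMRM model as described under sensitivity analysis in section" 5.3.3, also on the safety analysis set.

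**The concern.** Setting missing liraglutide outcomes to placebo level works against the drug when the drug is expected to help, and in its favour when the drug is expected to harm. Carrying the efficacy imputation over to pulse reverses its direction: each imputed liraglutide value moves the estimated rise toward zero.

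The rationale is also weakest where it would be needed most. Loss of effect after stopping cannot describe a type MT subject, who has not stopped. The imputation model in Table 5-3 uses baseline variables only, so a rise recorded at visits before the missing one is ignored.

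What is at stake is the only model-based estimate and confidence interval for a named risk, reported without any alternative handling of missing data beside it.

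**Working it through.** **1. The plan's own dilution rule.** Protocol 17.1 assumes that withdrawn subjects respond as if on placebo, and corrects by

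- Δ_corr = (1 − p)Δ
- σ²_corr = σ² + (2/3)p(1 − p)Δ²

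With Δ = 0.23 in absolute value, σ = 0.25 and p = 0.10:

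- Δ_corr = 0.9 × 0.23 = 0.207
- σ_corr = √(0.0625 + (2/3) × 0.09 × 0.0529) = 0.2563

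At two-sided 5%, 2:1 allocation and 80% power, a noncentral-t calculation gives 38 + 19 = 57 subjects (power 80.6%), as stated. The same calculation reproduces all 27 cells of Table 17-1. The plan therefore already counts on a shrinkage of (1 − p) under this imputation.

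**2. The same rule applied to pulse.** Inputs: a rise of 2-3 bpm (Protocol 18.1), and 10% withdrawal at week 16 and 20% at week 52 (Protocol 17.1). Assumption: missingness in the liraglutide arm is unrelated to pulse.

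| Visit | Share missing | True 2 bpm | True 3 bpm | Loss |
|---|---|---|---|---|
| Week 16 | 10% | 0.9 × 2 = 1.8 | 0.9 × 3 = 2.7 | 0.2-0.3 |
| Week 52 | 20% | 0.8 × 2 = 1.6 | 0.8 × 3 = 2.4 | 0.4-0.6 |

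**3. Simulation check.** Setting: 38 and 19 subjects, no covariates, random missingness in both arms, Rubin pooling, and a pulse SD of 10 bpm (assumed, because the documents give none). For a true 3 bpm, jump-to-reference averaged 2.69 at 10% missing and 2.35 at 20%. Analysing the observed values by arm gave 2.98 and 2.95. The mean ratio of estimate to standard error fell from 1.02 to 0.91 and from 0.96 to 0.74.

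**4. Size against the noise.** SE = SD × √(1/38 + 1/19) = 0.281 × SD. For assumed SDs of 8, 10 and 12 this is 2.2, 2.8 and 3.4 bpm. The loss of 0.2-0.6 bpm is then roughly 0.1-0.3 SE. Power to detect 3 bpm (normal approximation) is 27%, 19% and 14% with nothing missing, and 18%, 13% and 11% under jump-to-reference at 20% missing.

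**5. How much will be imputed.** The flow chart (Protocol section 2) schedules weight and height at V10x and V19x, but not pulse. An end-of-treatment pulse taken at an early stop is allocated to the window of the day it was taken (SAP 6.3.2.1). Early discontinuers will therefore usually lack a week-16 or week-52 pulse, and the imputed share may approach the rate of stopping trial product, which the documents do not give.

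**The case against.** The strongest defence is that the documents state no estimand for pulse. If the question is pulse by assigned arm whatever happens to treatment, a child off liraglutide may well be near placebo level, and the imputation is then defensible for drop-outs. That stands for type MD. It does not reach type MT, and the plan does not say that this is the question.

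It also stands that the effect is small beside the sampling error, that no formal claim rests on pulse (the hierarchical test covers only the two BMI SDS endpoints), and that the data are visible elsewhere. Summary and shift tables are planned with no imputation stated, clinically significant worsening must be reported as an adverse event (Protocol 8.5.3), ECG shifts are tabulated, and the data monitoring committee follows safety throughout.

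A reader might infer that the pulse signal is hidden, or that it would be cut far more severely because children with a fast pulse stop. The documents do not support either. The first is answered by the outputs just listed. For the second, they give no figure linking discontinuation to pulse, so only the direction can be stated.

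A reader might also infer that the amylase and lipase model can simply be copied as an on-treatment analysis. It cannot:

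- Those rows carry no on-treatment restriction. SAP Table 4-2 ends the on-treatment period for placebo at week 16, so such an analysis would have no week-52 comparator.
- Pulse is taken at 16 post-baseline visits (V4 to V19). The unstructured matrix of SAP 5.3.3 would need 16 × 17/2 = 136 parameters. SAP 5.1 requires part B alone to be analysed, with 24 subjects planned. With about 9 mean parameters per visit (if all four regions are represented), 24 − 9 = 15 residual degrees of freedom remain, too few for a 16 × 16 matrix even with complete data.

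**Conclusion.** The point holds as a modest, one-directional bias in the only modelled pulse estimate. At the plan's withdrawal rates the expected loss is 0.2-0.3 bpm at week 16 and 0.4-0.6 bpm at week 52. This rests on a true rise of 2-3 bpm, an imputed share equal to the assumed withdrawal rate, and missingness unrelated to pulse. With nothing missing there is no bias; if stopping is related to pulse, it could be larger by an amount the documents do not allow one to fix. This does not threaten the trial's conclusions on efficacy or conceal a risk. It merits correction because the efficacy rationale does not carry over to a harm, no sensitivity analysis stands beside the estimate, and the remedy is cheap.

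**What to change.** In SAP Table 5-5 row 27 and the Pulse paragraph of 5.4.1.3, make the main pulse analysis on the safety analysis set one that does not impute the liraglutide arm from placebo. Either of these would do:

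- ANCOVA with multiple imputation within randomised arm, using earlier pulse values in the imputation model.
- An MMRM limited to a few prespecified visits, for example weeks 4, 8, 16, 28, 40 and 52, with a stated fallback covariance structure.

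Use all observed control-arm values to week 52, and do not apply the Table 4-2 on-treatment definition to placebo. State in the row which question the estimate answers. Keep jump-to-reference at most as a supplementary analysis. Record the change in Appendix 2 (6.2.3), since Protocol 17.4.1.2 also points pulse to the blood pressure method.

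The cost is some extra programming and reliance on a missing-at-random assumption within arm. No new data are needed: pulse is already scheduled at these visits.

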## Laboratory parameters

Summary statistics will be tabulated for each laboratory parameter. The distributions will also be presented graphically using box plots by treatment and week.

For each laboratory parameter, the values will be compared to the relevant reference range. The results will be presented as follows:

- Shifts from baseline at 16 and 52 weeks will be tabulated. The shift tables will include the number of subjects below, within and above the reference range at each visit
- The proportion of subjects with laboratory values outside the reference range will be tabulated per visit and treatment group
- Individual values outside the reference range (abnormal values) will be listed by treatment and subject

For amylase and lipase the relative change ( $100 \times \text{value}/\text{baseline}$ ) will be analysed with an MMRM model as described under sensitivity analysis in section [5.3.3](#). The response and baseline values will be log transformed prior to the analysis. Safety analysis set will be considered. All lab parameters will be reported in standard units. However for the parameters like Total Cholesterol, LDL, HDL, Triglycerides, Total bilirubin, Creatinine, calcium, HbA1C, Fasting plasma glucose conventional units will also be provided along with standard units in the descriptive statistics output.

Box plots will be provided for lab parameters like Calcitonin, Lipase, Amylase, ALT, AST and Prolactin

## Pubertal status

Tanner stage at screening as well as changes in Tanner stage at 16 and 52 weeks will be summarised using descriptive statistics.

## Physical examination

Physical examination at screening and changes in physical examination will be summarised.

## Mental health questionnaires

Results from the mental health questionnaires PHQ-9 and C-SSRS from part A will be summarised using descriptive statistics and the frequencies of shifts from baseline to 16 and 52 weeks will be tabulated for each treatment group.

In addition to all the supportive secondary safety endpoints, following endpoints is added.

- Height) velocity in cm/year (if subject is still growing)

## Height velocity

Height velocity is the change in height per year and is measured in cm/year.

The height velocity is calculated as the difference between current height and baseline divided by time duration in days between those measurement time points and multiplied by 365 days.

### 5.5 Exploratory endpoints analysis

Not applicable

### 5.6 Other safety analyses

Not applicable

### 5.7 Other analyses

Not applicable

### 5.8 Interim analyses

No interim analysis is planned for the efficacy data in this trial. PK data from part A will be included in a population PK analysis also including historical data for other populations to aid dose selection for part B. Modelling results and safety data will be reviewed by the DMC before subjects in Part B will be enrolled in the trial. Before the randomisation code break for part A, modelling results will only be communicated to DMC and to individuals involved in dose selection for part B.

#### 5.8.1 Data monitoring committee

Refer section 12.7.2 from Protocol.

## 6 Supporting documentation

### 6.1 Appendix 1 List of abbreviations

AE	adverse event
ALT	alanine aminotransferase
AD	available drop-out
ANCOVA	analysis of covariance
AST	aspartate aminotransferase
AUC	area under the curve
AT	available on treatment
BMI	body mass index
BMI SDS	body mass index standard deviation score
BOCF	baseline observation carried forward
CI	confidence interval
CRF	case report form
C-SSRS	columbia suicidality severity rating scale
CV	coefficient of variance
FAS	full analysis set
DMC	data monitoring committee
HbA1c	glycosylated haemoglobin
hCG	human chorionic gonadotrophin
HDL	high density lipoprotein
hsCRP	high sensitivity C reactive protein
LDL	low density lipoprotein
LOCF	last observation carried forward
MD	missing drop-out
MedDRA	Medical Dictionary for Regulatory Activities
MI	multiple imputation
MMRM	mixed model for repeated measurements
MT	missing on treatment
PD	pharmacodynamics
PHQ-9	patient health questionnaire 9
PK	pharmacokinetics
SAE	serious adverse event
SAP	statistical analysis plan
SAS	safety analysis set
LAR	legally acceptable representative

## 6.2 Appendix 2: Changes to protocol-planned analyses

In this SAP the following changes is been made to the statistical consideration in the protocol are as elaborated below for:

### 6.2.1 Primary endpoints

- Due to the COVID-19 pandemic, the primary endpoint assessments (body weight and height) for very few subjects in part B could not be performed at the end of the double-blind period of the trial – Visit 10 (Week 16) or at the end of the open-label period of the trial – Visit 19 (Week 52). These measurements (missing or performed at home) will not be part of the primary analysis. An additional analysis will be performed by including the subjects impacted by COVID-19 at week16 and 52 for the change from baseline in BMI SDS.
- For the sensitivity analysis using LOCF method the protocol mentions that data from nominal visits (V10x and V19x) will not be used .Similarly for sensitivity analysis using BOCF, MMRM and week 16/52 completer analysis, data from nominal visits (10x and 19x) will be excluded.

